#### LFT ULN Shifts from Baseline to Worst Elevation

LFT ULN shifts from baseline to the worst (highest) on-treatment elevation will be summarized as the number and percentage of treated subjects in the following categories:  $\leq$  ULN, > ULN to  $\leq$  3 x ULN, > 3 x ULN to  $\leq$  5 x ULN, > 5 x ULN to  $\leq$  10 x ULN, > 10 x ULN to  $\leq$  20 x ULN, and > 20 x ULN (US and SI units are identical, U/L). LFTs will be limited to ALT and AST.

### **eDISH Scatter Plot**

An evaluation of drug-induced serious hepatotoxicity (eDISH) scatter plot will display the maximum TBL ratio of value to ULN on the y-axis versus the maximum ALT ratio of value to ULN on the x-axis by treatment group (excluding All BHV-3500), where both maxima will be on treatment but not necessarily concurrent. Both axes will be on the  $\log_{10}$  scale. Ratios < 0.1 x ULN will be set to 0.1. Sample sizes in the legend will represent subjects with paired ratios. A horizontal reference line will be placed at 2 x ULN, and a vertical reference line will be placed at 3 x ULN. The lower left quadrant will be labeled "Normal Range", the upper left quadrant will be labeled "Hyperbilirubinemia", the lower right quadrant will be labeled "Temple's Corollary", and the upper right quadrant will be labeled "Possible Hy's Law Range."

# 6.5.2.3 Laboratory Test Change From Baseline

Values and changes from baseline in laboratory tests will be summarized as continuous variables at baseline and the end of treatment visit.

## 6.5.3 Vital Signs and Physical Measurements

Vital signs will include systolic blood pressure, diastolic blood pressure, heart rate, temperature, and respiratory rate. In tables, only vital signs measured in the sitting position will be included.

Physical measurements will include weight and BMI.

A by-subject listing of vital signs and physical measurements will be provided for enrolled subjects.

## 6.5.3.1 Vital Sign and Physical Measurement Change From Baseline

Values and changes from baseline in vital sign and physical measurement parameters will be summarized as continuous variables at baseline and the end of treatment visit.

## 6.5.3.2 Vital Sign and Physical Measurement Abnormalities

On-treatment vital sign and physical measurement abnormalities will be summarized as the number and percentage of subjects in the following categories:

- Systolic blood pressure (mmHg): < 90, > 140, > 160
- Diastolic blood pressure (mmHg): < 50, > 90, > 100
- Heart rate (bpm): < 60, > 100
- Temperature (C): < 36, > 38
- Respiratory rate (breaths/min): < 12, > 20
- Weight change from baseline:  $\leq -7\%$ ,  $\geq 7\%$ .

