5.3 Exclusion Criteria

- 1. Disease Target Exclusion
 - a. Subjects with a history of basilar migraine or hemiplegic migraine.
- 2. Medical History and Concurrent Diseases
 - a. Subjects history of HIV disease.
 - b. Subject history with current evidence of uncontrolled, unstable or recently diagnosed cardiovascular disease, such as ischemic heart disease, coronary artery vasospasm, and cerebral ischemia. subjects with Myocardial Infarction (MI), Acute Coronary Syndrome (ACS), Percutaneous Coronary Intervention (PCI), cardiac surgery, stroke or transient ischemic attack (TIA) during the 6 months prior to screening.
 - c. Uncontrolled hypertension (high blood pressure), or uncontrolled diabetes (however, subjects can be included who have stable hypertension and/or stable diabetes for at least 3 months prior to being enrolled). A single blood pressure measurement of greater than 150 mm Hg systolic or 100 mm Hg diastolic after 10 minutes of rest is exclusionary.
 - d. Subject has a current diagnosis of major depression, other pain syndromes (e.g. chronic pelvic pain, chronic regional pain syndrome, fibromyalgia), psychiatric conditions (e.g., schizophrenia), dementia, or significant neurological disorders (other than migraine) that, in the Investigator's opinion, might interfere with study assessments.
 - e. Subject has a history of gastric, or small intestinal surgery (including Gastric Bypass, Gastric Banding, Gastric Sleeve, Gastric Balloon, etc.), or other disease or condition (e.g. chronic pancreatitis, ulcerative colitis, etc.) that causes malabsorption.
 - f. The subject has a history or current evidence of any significant and/or unstable medical conditions (e.g., history of congenital heart disease or arrhythmia, known suspected infection, hepatitis B or C, or cancer) that, in the Investigator's opinion, would expose them to undue risk of a significant adverse event (SAE) or interfere with assessments of safety or efficacy during the course of the trial.
 - g. Acute or chronic treatment with OTC or prescription nasal sprays. Subjects must stop all OTC/Rx nasal sprays 14 days prior to the screening visit and refrain from use until study completion.
 - h. History of nasal surgery in the 6 months preceding the screening visit.

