 - a. History of drug or other allergy which, in the opinion of the Investigator, makes the subject unsuitable for participation in the study.

4. Sex and Reproductive Status

- a. Females of child-bearing potential who are unwilling or unable to use an acceptable contraceptive method or abstinence to avoid pregnancy for the entire study period and for 90 days after the study.
- b. Women who are pregnant, lactating or breastfeeding.
- c. Women with a positive pregnancy test on enrollment or prior to study drug administration.

5. ECG and Laboratory Test Findings

- a. Estimated glomerular filtration rate (eGFR) according to the re-expressed abbreviated (four-variable) Modification of Diet in Renal Disease (MDRD) Study equation ≤ 40 ml/min/1.73m².
- b. Corrected QT interval > 470 msec (QTc by method of Frederica), at Screening.
- c. Left Bundle Branch block.
- d. Right Bundle Branch Block with a QRS duration ≥ 150 msec.
- e. Intraventricular Conduction Defect with a QRS duration ≥ 150 msec.
- f. Serum bilirubin (Total or Direct) $> 1 \times ULN$ (Only abnormal values of between 1-1.5x ULN may be repeated once for confirmation during the screening period).
- g. Neutrophil count $\leq 1000/\mu L$ (or equivalent).
- h. AST (SGOT) or ALT (SGPT) > 1 x ULN (Only abnormal values of between 1-1.5x ULN may be repeated once for confirmation during the screening period).
- i. HbA1c > 7%

6. Other Exclusion Criteria

- a. Prisoners or subjects who are involuntarily incarcerated.
- b. Subjects who are compulsorily detained for treatment of either a psychiatric or physical (e.g., infectious disease) illness.
- c. Participation in clinical trial with non-biological investigational agents or investigational interventional treatments within the 30 days prior to Baseline Visit.

- d. Subjects who have previously participated in any BHV-3500 study within the last 2 years.
- e. Participation in clinical trial with biological investigational agents within the 90 days prior to Baseline visit.
- f. Score of > 0 on the Sheehan Suicidality Tracking Scale for the period of 30 days prior to Screening and during the study.
- g. Participation in any other investigational clinical trial while participating in this clinical trial.
- h. Subjects must agree to provide all requested demographic information (i.e. gender, race).
- 7. Please see 5.4 for Prohibited medications and 5.4.1 for allowable Rescue Medications.

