### 6.5.4.3 ECG Abnormalities

On-treatment ECG abnormalities will be summarized as the number and percentage of subjects in the following categories:

- QTcB (msec): > 450, > 480, > 500
- OTcB interval increase from baseline (msec): > 30, > 60
- QTcF (msec): > 450, > 480, > 500
- QTcF interval increase from baseline (msec): > 30, > 60

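### The on-treatment vital-sign abnormality table ignores baseline, so pre-existing values are mixed with new ones and dilute them (minor, descriptive safety tables only)

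*SAP*

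**What the plan says.** SAP 6.5.3.2 sets the rule: "On-treatment vital sign and physical measurement abnormalities will be summarized as the number and percentage of subjects in the following categories". The blood pressure and heart rate rows are "Systolic blood pressure (mmHg): < 90, > 140, > 160", "Diastolic blood pressure (mmHg): < 50, > 90, > 100" and "Heart rate (bpm): < 60, > 100". Temperature (below 36, above 38) and respiratory rate (below 12, above 20) follow the same pattern. Only one row refers to the subject's own starting value: "Weight change from baseline", at 7% in either direction.

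Nothing elsewhere in the SAP supplies a baseline condition. Section 7.4 defines on-treatment purely by time, as after study drug start. Section 7.1.3 asks only for a value in the analysis period when the worst abnormality or category is tabulated; paired values are required for shift analyses, and none is planned for vital signs.

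On eligibility, Protocol 5.3 (criterion 2c) states: "A single blood pressure measurement of greater than 150 mm Hg systolic or 100 mm Hg diastolic after 10 minutes of rest is exclusionary". The same criterion admits subjects whose hypertension has been stable for at least 3 months.

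Two other vital-sign outputs are planned. Section 6.5.3.1 gives continuous summaries of values and of change from baseline, and section 6.5.3 gives a by-subject listing.

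**The concern.** A subject with a systolic pressure of 146 mmHg before dosing and 146 mmHg at the End of Treatment Visit has not changed, yet is counted in the above-140 row as an on-treatment abnormality. A subject who moved from 120 to 146 is counted in the same cell, and the table cannot tell them apart.

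The other safety domains in this SAP do make that distinction in categorical form:

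- laboratory tests have grade and low/normal/high shifts (6.5.2.1);
- ALT and AST have shifts in multiples of the upper limit of normal (6.5.2.2);
- ECG interpretation has a shift table (6.5.4.2) and QTc has increase categories (6.5.4.3);
- nasal inspection has shifts (6.5.6.2);
- adverse events have a treatment-emergent subset (7.6.1.3).

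Blood pressure, heart rate, temperature and respiratory rate have no such table. At stake is how readable the vital-sign safety summary is in a trial meant to help choose a dose for Phase 3.

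**Working it through.** **Step 1. Cut-offs against eligibility.** SAP 6.5.3.2 is compared with Protocol 5.3.

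| Row | Numeric eligibility limit | Can be met at entry? |
|---|---|---|
| Systolic > 140 | excluded only above 150 | yes (141 to 150) |
| Diastolic > 90 | excluded only above 100 | yes (91 to 100) |
| Systolic < 90, diastolic < 50 | none | yes |
| Heart rate < 60, > 100 | none | yes |
| Temperature < 36, > 38 | none | yes |
| Respiratory rate < 12, > 20 | none | yes |
| Systolic > 160 | excluded above 150 | no |
| Diastolic > 100 | excluded above 100 | no |
| Weight change of 7% or more | not applicable | already relative to baseline |

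Leaving weight aside, there are 3 + 3 + 2 + 2 + 2 = 12 cut-offs, and 12 − 2 = 10 of them can be met at entry.

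**Step 2. Size.** SAP 6.5.3.2 gives no figure to reproduce. The only document input is the group size, 0.95 × 400 = 380 (Protocol 9.2, SAP 5). That is the mITT count; safety tables use treated subjects, but the percentages below do not depend on it. The rest are assumptions:

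- b = share in the category at baseline;
- k = share of those still in it on treatment;
- q = new-onset rate among the others.

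Rate shown by the planned table = b·k + (1 − b)·q.

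With b = 10%, k = 50%, and q = 6% on drug and 3% on placebo:

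- Drug: 0.10 × 0.50 + 0.90 × 0.06 = 0.050 + 0.054 = 10.4%
- Placebo: 0.10 × 0.50 + 0.90 × 0.03 = 0.050 + 0.027 = 7.7%
- Ratio: 10.4 / 7.7 = 1.35, against 6.0 / 3.0 = 2.0 among subjects not in the category at baseline
- Carried-over share of the count: 0.050 / 0.104 = 48% on drug and 0.050 / 0.077 = 65% on placebo
- Difference: 10.4 − 7.7 = 2.7 points, against 3.0

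**Step 3. Range.** With the same new-onset rates, b from 5% to 30% and k from 50% to 70%:

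- the ratio in the planned table falls from 1.53 to 1.09;
- the carried-over share of the placebo count rises from 47% to 91%;
- the difference is 3.0 × (1 − b), that is 2.85 down to 2.1 points.

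**Step 4. Readability.** No test of vital signs is planned, so power serves only as a yardstick for how clearly a difference stands out. At a nominal two-sided 0.05 with 380 per group, the case in step 2 gives about 25% for the planned count and 47% for the count restricted to the 380 × 0.90 = 342 subjects not in the category at baseline.

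**The case against.** The strongest reply is that a baseline-referenced analysis already exists. SAP 6.5.3.1 summarizes change for every vital sign on paired values by treatment group, and the subject at 146 mmHg at both visits contributes a change of zero there. This stands in part: means and medians can miss a handful of individual shifts, and a listing is not a summary.

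A second reply is that the label is accurate. The SAP keeps on-treatment distinct from treatment-emergent, and placebo is shown alongside. This also stands: the percentages are correct for what they claim to count.

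A reader might go further and infer that new abnormalities are hidden. The documents do not support that. Randomization should balance carried-over values across groups, so the absolute difference shrinks only by the factor (1 − b); the ratio and the precision suffer more. Nor does the point cover every row, because systolic above 160, diastolic above 100 and weight change are largely unaffected. Having no numeric heart-rate limit does not mean that any heart rate is admitted either: inclusion criterion 4a bars clinically significant abnormalities, as judged by the investigator.

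A reader might also extend the point to QTcF, because SAP 6.5.4.3 counts "QTcF (msec): > 450, > 480, > 500" while Protocol 5.3 excludes "Corrected QT interval > 470 msec (QTc by method of Frederica), at Screening". The overlap is real, but that section already has rows for increases above 30 and 60 msec, and ECG parameters also have continuous change and an interpretation shift. No change is needed there.

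Finally, each subject takes one dose, and the only scheduled post-dose vital signs are at the End of Treatment Visit, which follows the 48-hour diary and falls within 7 (+2) days of dosing. The table can say little about short-lived effects, and the change proposed here does not alter that.

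**Conclusion.** The point holds as a minor one. The categorical vital-sign table does not separate new from pre-existing abnormalities, and 10 of its 12 vital-sign cut-offs can be met at entry by an eligible subject, most clearly systolic above 140 and diastolic above 90. New findings are diluted, not concealed.

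The illustration (10.4% versus 7.7% shown, 6.0% versus 3.0% new) rests on assumed prevalence, persistence and onset rates. The documents give none of these, so the true extent cannot be fixed in advance. The consequence is limited to descriptive safety tables. The safety objective names adverse events, serious adverse events and laboratory abnormalities, not vital signs, and no hypothesis test, alpha level or sample size depends on this table.

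**What to change.** In SAP 6.5.3.2, for each blood pressure, heart rate, temperature and respiratory rate category, add the number and percentage of subjects newly in that category. The denominator is subjects with paired baseline and on-treatment values who were not in that category at baseline, using the baseline definition in SAP 6.2.4. Apply the rule to each category separately, so that a subject going from 145 to 165 mmHg is new for the above-160 row but not for the above-140 row. A baseline-by-on-treatment shift table would serve equally well and would match the other safety domains. Keep the current all-subjects count beside it. Leave the weight rows and SAP 6.5.4.3 as they are.

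The cost is a sentence or two of SAP text and one programming condition, with no new data. The downside is that denominators differ from row to row and must be displayed.

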### 6.5.4 Electrocardiogram

ECG parameters will include RR, QRS, PR, QT, QTcF, and ventricular heart rate.

A by-subject listing of ECG results will be provided for enrolled subjects.

### 6.5.4.1 ECG Change from Baseline

Values and changes from baseline in ECG parameters will be summarized as continuous variables at baseline and the end of treatment visit.

### 6.5.4.2 ECG Interpretation Shift from Baseline to Worst Category

The ECG interpretation shift from baseline to the worst on-treatment category will be summarized as the number and percentage of subjects with normal, abnormal, and clinically significant abnormal interpretations.

### 6.5.4.3 ECG Abnormalities

On-treatment ECG abnormalities will be summarized as the number and percentage of subjects in the following categories:

- QTcB (msec): > 450, > 480, > 500
- OTcB interval increase from baseline (msec): > 30, > 60
- QTcF (msec): > 450, > 480, > 500
- QTcF interval increase from baseline (msec): > 30, > 60

# 6.5.5 Sheehan-Suicidality Tracking Scale (S-STS)

The S-STS is a prospective, self-reported rating scale that contains 16 questions to track both treatment-emergent suicidal ideation and behaviors. In the event the subject is unavailable, the S-STS clinician-administered rating scale will be completed that contains 6 yes/no questions.

Self-reported S-STS scores are calculated as follows:

- Ideation subscale score: Sum of scores (0-4) for Questions 2-11
- Behavior subscale score: Sum of scores (0-4) for Questions 1a, (highest of 12 or any row of 16), (highest of 14 or any row of 15), 17, and 20
- Total score: Sum of the ideation and behavior subscale scores.

Values and changes from baseline in the self-reported S-STS ideation subscale, behavior subscale, and total score will be summarized as continuous variables at baseline and the end of treatment visit. The number and percentage of subjects in each change from baseline category (i.e., < -1, -1, no change, 1, > 1) will also be presented for the ideation subscale, behavior subscale, and total score.

The by-subject S-STS listing will include study visit and assessment date. If the total score > 0, then responses to all questions will be presented; otherwise, only the ideation subscale, behavioral subscale, and total scores will be presented.

# 6.5.6 Nasal Inspection

Nasal inspections will evaluate evidence of edema and inflammation in the left and right nostrils with yes or no responses. Abnormalities are considered to be "yes" responses.

A by-subject listing of nasal inspection will be provided for enrolled subjects.

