¹ Screening Phase will be 3 - 28 days. Subject should be entered in the IWRS once they sign the informed consent form to obtain their study subject identification code.

²The **Baseline**/ **Randomization Visit** may only occur *after* all screening procedures are completed and the subject meets all inclusion/exclusion criteria. If the subject does not meet all eligibility requirements, the subject should be screen failed in the IWRS.

³ Subjects will use their assigned eCOA handheld device to answer questions about their migraine symptoms upon experiencing a moderate or severe migraine headache. The subject will administer study drug or matching placebo if the following criteria are met: 1) the headache remains moderate or severe; 2) the subject has completed all required migraine assessment questions in the handheld, including their current most bothersome migraine symptom, and 3) the subject has not already taken prohibited medications (see protocol section 5.4).

⁴ Subjects should keep track of their concomitant and rescue medications on the appropriate study paper diary provided throughout the study. These diaries should be returned to the investigational site for review and electronic data capture (EDC) entry.

⁵ The randomization visit is considered day 1 out of the 45 days subjects have to treat and report a migraine in their handheld device. Subjects will be randomized in the IWRS and will be stratified by answering "yes" or "no" to prophylactic migraine medication use in the IWRS.

⁶Nasal inspection – The nasal passages and turbinates will be visually inspected with a nasal speculum or otoscope at the screening, baseline and end of treatment visits to detect evidence of nasal inflammation or edema.

⁷ Height will only be captured at the Screening Visit. Weight, body temperature, respiratory rate, blood pressure and heart rate will be collected at all time points where indicated. Sitting arterial systolic and diastolic blood pressure and pulse rate will be measured.

- ⁸ SAEs are reported from the time of signed informed consent and non-serious AEs are reported from baseline. All ongoing non-serious AEs and SAEs will be followed to resolution or until the Investigator deems there will be no further status change. SAEs that occur during the treatment period should be reported to site in real time. Non-serious AEs that occur during the treatment period should be reported to the site at the EOT.

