6.2.3.1 Nasal Inspection

The nasal passages and turbinates will be visually inspected by the Investigator or medically qualified delegate with a nasal speculum or otoscope at the screening, baseline and end of treatment visits to detect evidence of significant nasal conditions that may affect the administration or absorption of the nasal product (e.g. severe septum deviation, nasal deformity or blockage, inflammation, perforation, mucosal erosion or ulceration, polyposis, nasal trauma). Nasal findings will be recorded as appropriate and followed until resolution.

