# 6.5.1.3 On-Treatment AEs by SOC and PT

On-treatment AEs will be summarized by SOC and PT for treated subjects for the following endpoints:

- AEs by severity
- TEAEs by severity
- AEs related to study drug by severity
- SAEs
- AEs leading to study drug discontinuation
- Hepatic-related AEs \*
- Cardiovascular AEs \*
- Suicidality AEs \*.

AEs of special interest are asterisked ("\*").

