# 6.5.6.1 Nasal Inspection Abnormalities

On-treatment nasal inspection abnormalities will be summarized for each parameter as the number and percentage of subjects with abnormalities for the following parameters: nasal edema or nasal inflammation in either nostril; nasal edema in left nostril; nasal edema in right nostril; nasal inflammation in left nostril; nasal inflammation in right nostril. Percentages will be based on subjects with non-missing data for each parameter.

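### The SAP's nasal inspection tables have rows only for edema and inflammation, and the protocol itself gives two different scopes for that inspection

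*SAP*

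**What the plan says.** Two protocol texts describe one inspection, made with a speculum or otoscope at screening, baseline and end of treatment.

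- Protocol 6.2.3.1 has the examiner look for significant conditions that could affect administration or absorption of the product. Its examples are "severe septum deviation, nasal deformity or blockage, inflammation, perforation, mucosal erosion or ulceration, polyposis, nasal trauma". Findings are to be recorded as appropriate and followed to resolution.
- Protocol 4.3, Table 1 footnote 6, says the inspection at the same visits is "to detect evidence of nasal inflammation or edema".

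The SAP takes the narrower scope. Section 6.5.6 reads "Nasal inspections will evaluate evidence of edema and inflammation in the left and right nostrils with yes or no responses" and counts a yes as an abnormality. Section 6.5.6.1 tabulates five on-treatment parameters, starting with "nasal edema or nasal inflammation in either nostril; nasal edema in left nostril; nasal edema in right nostril"; the other two are inflammation in each nostril. Section 6.5.6.2 tabulates shifts from baseline for the four nostril-specific items. A by-subject listing is planned, but the SAP does not say that it shows anything beyond these items.

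**The concern.** The product is a nasal spray, and an aim of the trial is to identify an optimal dose among three. Protocol 3.3 lists nasal inspection among the safety and other assessments. SAP 6.5.6 is the only analysis in the plan devoted to the nasal examination.

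If an examiner sees a new erosion, ulcer or perforation at the end of treatment, these tables have nowhere to put it. A difference between doses in such findings could not be read from them. The reader would have to reconstruct it from adverse event terms, and only to the extent that sites reported the findings as events.

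**Working it through.** No alpha, power, rate or sample size enters this point, and the plan states no figure to reproduce. The check compares the texts and then follows individual subjects through the tables.

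**Step 1: scope of each text**

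| Text | Edema | Inflammation | Perforation, erosion or ulceration, trauma |
|---|---|---|---|
| Protocol 6.2.3.1 (examples) | not named | yes | yes |
| Protocol Table 1 footnote 6 | yes | yes | no |
| SAP 6.5.6, 6.5.6.1, 6.5.6.2 | yes | yes | no |

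Separated at the commas, 6.2.3.1 gives seven examples. One of the seven, inflammation, is named in a SAP row. The SAP agrees with the footnote and not with 6.2.3.1, so the inconsistency starts inside the protocol.

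**Step 2: the denominator**

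SAP 6.5.6.1 says "Percentages will be based on subjects with non-missing data for each parameter". Each row percentage is therefore the number of subjects with a yes divided by the number with any answer to that item.

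**Step 3: subjects with a new lesion at the end of treatment, all items no at baseline**

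| Edema and inflammation answers | Abnormality table (five rows) | Shift table (four items) |
|---|---|---|
| No to all, both nostrils | adds 0 to every numerator and 1 to every denominator | no to no for all four |
| Yes to inflammation in one nostril, no otherwise | counted in the either-nostril row and that nostril's inflammation row; lesion not identified | no to yes for one item; lesion not identified |

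In the first case the subject is tabulated as not abnormal. In the second the subject looks the same as one with inflammation alone.

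**Step 4: the other route into the results**

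Protocol section 8 counts any unfavorable and unintended sign as an adverse event, and says events may be elicited by examination. SAP 6.5 and 6.5.1.3 tabulate on-treatment events by system organ class and preferred term, by dose received. SAP 7.6.1.2 counts each subject once per class. A reported lesion therefore does reach the safety tables.

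The weak link is whether it is reported. Protocol 8.2.2 states which laboratory abnormalities must be entered as events. No such rule exists for nasal findings, only the recording instruction in 6.2.3.1. AE capture is thus expected but not systematic in the way a yes/no item asked of every subject would be.

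**The case against.** The case for leaving the plan alone has real substance.

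- **The SAP has a protocol basis.** It follows footnote 6. This stands: the fault is a conflict within the protocol that the SAP resolved in one direction without saying what happens to other findings.
- **The 6.2.3.1 list is about suitability for dosing.** It is framed around administration and absorption, and the same examples appear in exclusion criterion 2.i. This stands for screening and baseline. It explains the end-of-treatment inspection poorly, because each subject takes a single spray and nothing remains to be administered. Since criterion 2.i excludes significant conditions of this kind at screening, one seen at the end is likely to be new.
- **Adverse event tables cover new lesions.** This largely stands, subject to the reporting gap described above. The class-level rows could show a dose pattern.
- **The CRF is not among the documents.** It may already hold a field for other findings. This also stands, but the SAP gives no summary that would use one.

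A reader might infer that the SAP hides the more serious local lesions, or that the trial's main local-tolerability table would report a clean result while they are present. The documents do not support that. Neither document ranks these findings by seriousness. The tolerability objective is defined by adverse events of at least moderate intensity, serious adverse events and laboratory abnormalities, not by nasal inspection. A lesion left out of the nasal tables is not thereby lost from the safety results.

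**Conclusion.** The point holds in a limited form. Protocol 6.2.3.1 and Table 1 footnote 6 describe the same inspection differently, and the SAP's abnormality and shift tables have no category for anything but edema and inflammation. Within those tables a lesion without either sign is counted as not abnormal, and a lesion with either sign is not identified.

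The size is unknown. The documents give no rate for such lesions, and any count per arm would rest on a guess. The co-primary analyses are unaffected. The conclusion assumes that the CRF collects what SAP 6.5.6 describes; if it has a further field, only the SAP tables and the protocol wording need attention. This is an inexpensive improvement to local safety reporting and does not show that safety data would be lost.

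**What to change.** 1. Reconcile Protocol Table 1 footnote 6 with 6.2.3.1, so that one scope applies to the inspection at each visit.
2. Add a yes/no item for other significant nasal findings to the nasal inspection CRF, with erosion or ulceration, perforation, and other (specify) as its options.
3. Carry that item into SAP 6.5.6.1 and 6.5.6.2, and include it in a row for any nasal abnormality.
4. If the CRF can no longer change, state in the SAP that such findings are reported as adverse events, and summarise them by dose using a list of nasal preferred terms fixed before unblinding.

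An additional adverse-event-of-special-interest category would be the sponsor's choice and is not needed for this. The cost is a few CRF fields and table rows for an examination already being done, with no new visit or procedure.
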